MedDRA	Medical dictionary for regulatory activities
██████████	████████████████████
MTD	Maximum Tolerated Dose

NeuPSIG	Neuropathic Pain Special Interest Group
NPSI	Neuropathic Pain Symptom Inventory
NRS	Numeric Rating Scale
NSAID	Nonsteroidal Anti-inflammatory Drugs
OATP1B1	Organic Anion Transporter Protein 1B1
OATP1B3	Organic Anion Transporter Protein 1B3
OC/RDC	Oracle Clinical/Remote Data Capture
OCT2	Organic Cation Transporter 2
PCR	Protein-Creatinine Ratio
PDN	Painful Diabetic Neuropathy
PerfO	Performance Outcomes
PHN	Post-Herpetic Neuralgia
PK	Pharmacokinetics
PGIC	Patient Global Impression of Change
PRO	Patient Reported Outcome
PRN	pro re nata (as needed)
PT	Prothrombin Time
QM	Quality Management
█	█
QTc	Corrected QT interval
QTcF	Fridericia QT correction formula
SAD	Single Ascending Dose
SAE	Serious Adverse Event
SAF	Safety set
█	█
SOP	Standard Operating Procedure
SSRI	Selective Serotonin Reuptake Inhibitor
SUSAR	Suspected Unexpected Serious Adverse Reactions
TD	Study Treatment Discontinuation
TENS	Transcutaneous Electrical Nerve Stimulation
TEAE	Treatment-Emergent Adverse Events
UGT	Uridine Diphosphate Glycosyltransferase
ULN	Upper limit of Normal
US	United States
VRS	Verbal Rating Scale
WHO	World Health Organization
WoC	Withdrawal of Consent

Glossary of terms

Cohort/arm	A specific group of patients/subjects fulfilling certain criteria
Control drug	Drugs(s) used as a comparator to reduce assessment bias, preserve blinding of investigational drug, assess internal study validity, and/or evaluate comparative effects of the investigational drug
Dosage	Dose of the study treatment given to the patient in a time unit (e.g. 100 mg once a day, 75 mg twice a day)
Electronic Data Capture (EDC)	Electronic data capture (EDC) is the electronic acquisition of clinical study data using data collection systems, such as Web-based applications, interactive voice response systems and clinical laboratory interfaces. EDC includes the use of Electronic Case Report Forms (eCRFs) which are used to capture data transcribed from paper source forms used at the point of care.
Enrollment	Point/time of patient entry into the study at which informed consent must be obtained (e.g. prior to starting any of the procedures described in the protocol)
Epoch	A portion of the study which serves a specific purpose. Epochs in this study are: screening, treatment, and treatment withdrawal
Investigational drug	The drug whose properties are being tested in the study; this definition is consistent with US CFR 21 Section 312.3 and is synonymous with “investigational new drug” or “investigational medicinal product.”
Medication pack number	A unique identifier on the label of each investigational drug package
Patient/subject ID	A unique number assigned to each patient upon signing the informed consent
Randomization number	A unique identifier assigned to each randomized patient, corresponding to a specific treatment arm assignment
Source Data/Document	Source data refers to the initial record, document, or primary location from where data comes. The data source can be a database, a dataset, a spreadsheet or even hard-coded data, such as paper or eSource.
Study drug/treatment	Any single drug or combination of drugs administered to the patient as part of the required study procedures; includes investigational drug (s), placebo/comparator active drug run-ins or background therapy
Study Treatment Discontinuation (TD)	When the patient permanently stops taking study treatment prior to the defined study treatment completion date
Variable	A measured value or assessed response that is determined in specific assessments and used in data analysis to evaluate the drug being tested in the study
Withdrawal of consent (WoC)	Withdrawal of consent from the study is defined as when a patient does not want to participate in the study any longer, and does not want any further visits or assessments, and does not want any further study related contact, and does not allow analysis of already obtained biologic material

Protocol summary

Protocol number	CEMA401A2202
Full Title	A double-blind, placebo-controlled, randomized trial to determine the safety and efficacy of EMA401 100 mg b.i.d. in reducing 24-hour average pain intensity score in patients with painful diabetic neuropathy (EMPADINE)
Brief title	Safety and efficacy of EMA401 in patients with painful diabetic neuropathy (PDN)
Sponsor and Clinical Phase	Novartis Phase 2
Investigation type	Drug
Study type	Interventional
Purpose and rationale	The purpose of this study is to evaluate safety and efficacy of EMA401 100 mg b.i.d. compared to placebo in patients with painful diabetic neuropathy (PDN).
Primary Objective(s)	To compare the efficacy of EMA401 vs. placebo in 24-hour average pain intensity score at Week 12, using an 11 point Numeric Rating Scale (NRS) by testing the superiority of EMA401 100 mg b.i.d vs. placebo
Key secondary Objective	To compare the efficacy of EMA401 vs. placebo in Neuropathic Pain Symptom Inventory (NPSI) total score by testing the superiority of EMA401 100 mg b.i.d vs. placebo
Secondary Objectives	
 • Objective 1: To evaluate the efficacy of EMA401 compared to placebo, as measured by the Brief Pain Inventory-Short Form (BPI-SF) interference total score at Week 12 • Objective 2: To evaluate the efficacy of EMA401 compared to placebo, as measured by the weekly mean of the 24-hour worst pain intensity score, using an 11-point Numeric Rating Scale (NRS) at Week 12 • Objective 3: To evaluate the efficacy of EMA401 compared to placebo, on the Patient Global Impression of Change (PGIC) at Week 12 • Objective 4: To evaluate the proportion of EMA401 patients achieving a $\geq 30\%$ and a $\geq 50\%$ reduction in weekly mean 24-hour average pain intensity score using the NRS compared to placebo (i.e., responder rates) at Week 12 • Objective 5: To evaluate the effect of EMA401 compared to placebo on the Insomnia Severity Index (ISI) at Week 12 • Objective 6: To evaluate the safety and tolerability of EMA401 compared to placebo in PDN patients, as measured by treatment-emergent adverse events (TEAEs), adverse events (AEs) leading to study drug discontinuation and serious adverse events (SAEs) throughout the study • Objective 7: To evaluate the pharmacokinetics (PK) of EMA401 and exposure-response (decrease in pain intensity) relationship for EMA401 throughout the study • Objective 8: To evaluate the proportion of patients who need rescue medication separately for the double blind treatment epoch and treatment withdrawal epoch and the time to first intake of rescue medication during the double blind treatment epoch.
Study design	The study is interventional, randomized, parallel, placebo-controlled,

	double-blind treatment.
Population	The study population will consist of approximately 400 randomized male and female patients (≥ 18 years old) with PDN
Key Inclusion criteria	
 At the time of Screening, have documented diagnosis of Type I OR Type II diabetes mellitus (DM) with painful distal symmetrical sensorimotor neuropathy (for example ICD-10 code G63.2) of more than 6 months duration with any one or more of the following: 
 Neuropathic symptoms (e.g. numbness, non-painful paresthesias or tingling, non-painful sensory distortions or misinterpretations, etc.) Decreased distal sensation (e.g. decreased vibration, pinprick sensation, light touch, etc.) Be assessed as suffering from moderate to severe neuropathic pain across the Screening epoch (NRS ≥ 4) A score of ≥ 4 on the Douleur Neuropathique en 4 Questions (DN4) questionnaire at Screening
Key Exclusion criteria	
 History or current diagnosis of electrocardiogram (ECG) abnormalities indicating significant risk of safety for patients participating in the study Major depressive episode within 6 months prior to Screening and/or a history of diagnosed recurrent major depressive disorder according to Diagnostic and Statistical Manual of Mental Disorders, 5th Edition (DSM-V) diagnostic criteria Have evidence of significant renal insufficiency or pre-existing liver condition Have platelets ≤ 100 x 10⁹/L, or neutrophil count < 1.2 x 10⁹/L (or equivalent), hemoglobin ≤ 100 g/L for women or hemoglobin ≤ 110 g/L for men Participants whose glycemic control has been unstable within 3 months immediately prior to screening (e.g., ketoacidosis requiring hospitalization, any recent episode of hypoglycemia requiring assistance through medical intervention, uncontrolled hyperglycemia) Patients with any differential diagnosis of PDN including but not limited to other neuropathies (e.g. Vitamin B12 deficiency, Chronic Inflammatory Demyelinating Polyneuropathy), polyradiculopathies, central disorders (e.g. demyelinating disease), or rheumatological disease (e.g., foot arthritis, plantar fasciitis) Patient is unwilling or unable to complete daily eDiary
Study treatment	EMA401 and placebo
Efficacy assessments	
 11-point Numeric Rating Scale (NRS) Neuropathic Pain Symptom Inventory (NPSI) Brief Pain Inventory-Short Form (BPI-SF) Patient Global Impression of Change (PGIC) Insomnia Severity Index (ISI)
Key safety assessments	
 Adverse event monitoring Physical examinations and vital signs Monitoring of laboratory markers in blood and urine ECGs

	
• Withdrawal and rebound effect
Other assessments	
• Pharmacokinetics (PK)
█ [REDACTED]█ [REDACTED]█ [REDACTED]█ [REDACTED]
Data analysis	
The primary objective of the study will be achieved if the active dose (EMA401 100 mg b.i.d.) is statistically significant versus placebo in terms of 24-hour average pain intensity score at Week 12, using an 11 point Numeric Rating Scale (NRS).
 
Similarly, key secondary objective of the study will be achieved if the active dose (EMA401 100 mg b.i.d.) is statistically significant versus placebo in terms of Neuropathic Pain Symptom Inventory (NPSI) total score.
 
While comparing EMA401 100 mg b.i.d. versus placebo, for the primary and key secondary endpoints the statistical testing will be carried out using the graphical testing procedure to preserve the family-wise error rate at the 2.5% level.
 
The estimation of the treatment effect will be performed based on an Analysis of Covariance (ANCOVA) model including region (e.g. US, EU), treatment, sex, use of concomitant pain medication for PDN (yes/no) as factors and baseline score and age as covariates. The analysis will account for different post-randomization events, such as changes in doses of concomitant medication for PDN, intake of rescue medication, intake of prohibited medications that have a potential confounding effect on efficacy of the investigational drug, and discontinuations of study treatment due to different reasons.

Key words	Painful diabetic neuropathy, neuropathic pain, angiotensin II type 2 receptor antagonist

1 Introduction

1.1 Background

Neuropathic pain is recognized as having one of the most significant unmet needs of all the various forms of chronic pain. Painful diabetic neuropathy (PDN) is the most prevalent type of neuropathic pain, affecting up to 50% of diabetic patients ([Mixcoatl-Zecuatl and Calcutt 2013](#)). It is estimated that there will be over 8 million prevalent cases of PDN in US and Europe by the end of 2016, with 2.5% annual growth rate to reach 10 million cases by 2024 ([Kravit and Kuranz 2015](#)). The next most prevalent forms of neuropathic pain are HIV/AIDS-related neuropathy, neuropathic cancer pain and post-herpetic neuralgia (PHN). The latter two affect over 0.5 million patients each and the proportion of patients is expecting to grow at 1.4% annual growth rate till 2024. About 20% of patients with herpes zoster report some pain at 3 months after the onset of symptoms, and 15% report pain at 2 years ([Johnson and Rice 2014](#)). Neuropathic cancer pain is experienced by 29% of people living with inoperable cancer ([Kravit and Kuranz 2015](#)).

Diabetic neuropathy is a common and disabling complication of diabetes mellitus (DM) and has been recognized as a leading cause of non-traumatic amputations secondary to foot ulceration ([Vinik et al 2000](#); [Mahmood et al 2009](#)). The typical diabetic neuropathy is a chronic, symmetrical, length-dependent sensory-motor polyneuropathy. Though the precise etiology of diabetic neuropathy remains to be elucidated, it develops on a background of long-standing metabolic dysfunction associated with diabetes (including polyol flux, hyperglycemia, accumulation of advanced glycation end products, oxidative stress, and lipid alterations among other metabolic abnormalities) and cardiovascular risk factors ([Dyck et al 1999](#); [Tesfaye et al 2005](#); [Dyck et al 2006](#)). The neuropathy in diabetes can affect the peripheral (painful diabetic neuropathy; PDN) nervous system or the autonomic nervous system (diabetic autonomic neuropathy); the current study focuses exclusively on the former.

Pain is a common complication of diabetic neuropathy and the condition, PDN, has few validated treatments. The patient complains of pain which is distal, symmetrical, often associated with nocturnal exacerbations, and commonly described as prickling, deep aching, sharp, like an electric shock, or burning with hyperalgesia and frequently allodynia upon examination ([Apfel et al 2001](#); [Boulton et al 2004](#)).

Recent recommendations of Neuropathic Pain Special Interest Group (NeuPSIG) for the pharmacotherapy of neuropathic pain include use of tricyclic antidepressants, serotonin-noradrenaline reuptake inhibitors (i.e. duloxetine), pregabalin, and gabapentin as first line agents ([Finnerup et al 2015](#)). Recommended second line therapy includes lidocaine patches, capsaicin high-concentration patches, and tramadol. These treatments however work in a subset of the patient population; significant proportion of patients get $\leq 50\%$ pain reduction and are accompanied by side effects that limit their utility ([Hempstead et al 2005](#)). High-dose monotherapy or combination of existing therapies is often used in patients with inadequate pain control in clinical practice. However, the benefit of the combination of currently available first or second line agents is limited due to additional tolerability issues, and disadvantages of combinations often outweigh the benefits. The majority of combinations

evaluated to date involve drugs which share some element of central nervous system (CNS) depression (e.g. sedation, cognitive dysfunction). This aspect of side effect overlap between combinations results in high treatment discontinuation rates and thus may substantially limit the utility of such combinations (Chaparro et al 2012). Given the prevalence and severity of PDN, a clear need exists for better treatments to reduce the condition's burden on patients and society.

EMA401 is an angiotensin II type 2 (AT₂) receptor antagonist that has been shown to be active in established animal and clinical neuropathic pain models (Rice et al 2014; Smith and Muralidharan 2015). Initial safety data for EMA401 has been generated in seven Phase 1 studies and one open label Phase 2 study in Chemotherapy Induced Neuropathic Pain (CINP). Additionally, a randomized, placebo-controlled, multi-centric, proof of concept Phase 2 efficacy study in PHN patients was completed, in which patients on EMA401 (100 mg b.i.d.) reported significant improvement in pain intensity compared to placebo following four weeks of treatment (Rice et al 2014). EMA401 was well-tolerated and demonstrates a positive benefit risk profile based on all evidence generated to date.

1.2 Purpose

The purpose of this study is to evaluate safety and efficacy of EMA401 100 mg b.i.d. (i.e. 200 mg/day) compared to placebo in patients with painful diabetic neuropathy (PDN).

[figure not shown]
2 Study objectives and endpoints

[figure not shown]
2.1 Objectives and related endpoints

Table 2-1 Objectives and related endpoints

Objective(s)	Endpoint(s)

Primary Objective(s)
 
 To compare the efficacy of EMA401 vs. placebo in 24-hour average pain intensity score at Week 12, using an 11 point Numeric Rating Scale (NRS) by testing the superiority of EMA401 100 mg b.i.d. vs. placebo 	
Endpoint(s) for primary objective(s)
 
 Change in weekly mean 24-hour average pain score (using the 11 point NRS) from Baseline to Week 12

Key Secondary Objective(s)
 
 To compare the efficacy of EMA401 vs. placebo in Neuropathic Pain Symptom Inventory (NPSI) total score by testing the superiority of EMA401 100 mg b.i.d. vs. placebo 	
Endpoint(s) for key secondary objective(s)
 
 Change in Neuropathic Pain Symptom Inventory (NPSI) total score from Baseline to Week 12

Secondary Objective(s)
 
 To evaluate the efficacy of EMA401 compared to placebo, as measured by the Brief Pain Inventory-Short Form (BPI-SF) interference total score at Week 12 To evaluate the efficacy of EMA401 compared to placebo, as measured by 	
Endpoint(s) for secondary objective(s)
 
 Change in BPI-SF interference total score from Baseline to Week 12 Change in weekly mean of the 24-hour worst pain score, using an 11-point NRS,

Objective(s)	Endpoint(s)

the weekly mean of the 24-hour worst pain intensity score, using an 11-point Numeric Rating Scale (NRS) at Week 12
 
• To evaluate the efficacy of EMA401 compared to placebo, on the Patient Global Impression of Change (PGIC) at Week 12• To evaluate the proportion of EMA401 patients achieving a $\geq 30\%$ and a $\geq 50\%$ reduction in weekly mean 24-hour average pain intensity score using the NRS compared to placebo (i.e., responder rates) at Week 12• To evaluate the effect of EMA401 compared to placebo on the Insomnia Severity Index (ISI) at Week 12• To evaluate the safety and tolerability of EMA401 compared to placebo in PDN patients, as measured by treatment-emergent adverse events (TEAEs), adverse events (AEs) leading to study drug discontinuation and serious adverse events (SAEs) throughout the study• To evaluate the pharmacokinetics (PK) of EMA401 and exposure-response (decrease in pain intensity) relationship for EMA401 throughout the study• To evaluate the proportion of patients who need rescue medication separately for the double blind treatment epoch and treatment withdrawal epoch and the time to first intake of rescue medication during the double blind treatment epoch.	
from Baseline to Week 12
 
• PGIC at Week 12• Proportion of patients meeting responder criteria from Baseline to Week 12• Change in ISI from Baseline to Week 12• Number and severity of treatment-emergent adverse events and the frequency of adverse events leading to discontinuation. Number of serious adverse events.• Plasma pharmacokinetics of EMA401 will be characterized by population non-linear mixed effects modeling techniques• Proportion of patients who need rescue medication separately for the double blind treatment epoch and treatment withdrawal epoch, the time to first intake of rescue medication during the double blind treatment epoch

3 Investigational plan

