			
 Analyses of AEs have been reduced. No subgroup analyses and analyses of drug-related AEs will be provided Dot plots and Kaplan Meier plots of AEs have been removed 	2.8.1.2 Liver events

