List of abbreviations

ACR	Albumin-Creatinine Ratio
AE	Adverse Event
ALP	Alkaline Phosphate
ALT	Alanine Aminotransferase
ANCOVA	Analysis of covariance
AST	Aspartate Aminotransferase
ATC	Anatomic Therapeutic Chemical classification
b.i.d.	twice a day
BPI-SF	Brief Pain Inventory-Short Form
CRO	Contract Research Organization
CSR	Clinical Study Report
DAR	Dose Administration Record
DMC	Data Monitoring Committee
DN4	Douleur Neuropathique en 4 Questions
ECG	Electrocardiogram
eCRF	Electronic Case Report Form
e-diary	Electronic diary
EU	European Union
FAS	Full Analysis Set
FDA	Food and Drug Administration
GGT	gamma-glutamyltransferase
HIV	Human Immunodeficiency Virus
INR	International Normalized Ratio
IRT	Interactive Response Technology
ISI	Insomnia Severity Index
J2R	Jump to reference
LFT	Liver function test
LoE	Lack of efficacy
MAR	Missing at random
mFAS	Modified Full Analysis Set
MedDRA	Medical dictionary for regulatory activities
NPSI	Neuropathic Pain Symptom Inventory
NRS	Numeric Rating Scale
NSAID	Nonsteroidal Anti-inflammatory Drugs
PCR	Protein-Creatinine Ratio
PDN	Painful Diabetic Neuropathy

PHN	Post-Herpetic Neuralgia
PK	Pharmacokinetics
PGIC	Patient Global Impression of Change
PRO	Patient Reported Outcome
█	█
QTc	Corrected QT interval
QTcB	Bazett QT correction formula
QTcF	Fridericia QT correction formula
SAE	Serious Adverse Event
RDO	Retrieved drop-out
SAF	Safety population
█	█
SSRI	Selective Serotonin Reuptake Inhibitor
TBL	Total bilirubin
TD	Study Treatment Discontinuation
TEAE	Treatment-Emergent Adverse Events
ULN	Upper limit of Normal
USM	Urgent Safety Measures
VRS	Verbal Rating Scale
WHO	World Health Organization

Amendment 1

This amendment of the statistical analysis plan (SAP) is largely based on changes induced due to the early termination of the CEMA401A2202 study. 137 patients out of 400 planned patients have been randomized. As the number of patients included in the study is considerably reduced, an abbreviated Clinical Study Report (CSR) that still meets all requirements for reporting and disclosure of the demographics, primary endpoint, secondary endpoints and safety results to public registries will be created.

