The primary analysis on the change from baseline to Week 12 in the weekly mean of the 24-hour average pain score will be performed as originally planned. Besides the primary estimand, which is of main clinical interest, the supplementary estimand, which provides insight into the magnitude of improvement in efficacy that might be achieved if all patients were able to take EMA401 as prescribed for 12 weeks, will be analysed. The other planned supplementary estimands will be dropped, as they are of minor interest in the situation with many study treatment discontinuations due to trial termination in the scope of the Urgent Safety Measures (USM).

To support the primary analysis and to get an idea about the effect that might be achieved if the trial had not been terminated and if all patients had the chance to complete the Week 12 assessment, a sensitivity analysis on a modified population will be performed. The modified full analysis set will include all patients who had a chance to complete the study before the termination date, i.e. who had been randomized at least 12 weeks before study termination date.

Similar considerations were made for the key-secondary endpoint.

Due to the considerably reduced number of patients who completed the study, only descriptive subgroup analyses will be provided. Moreover, the secondary endpoints will also be summarized descriptively only.

1 Introduction

This statistical analysis plan (SAP) describes all planned analyses for the Clinical Study Report (CSR) of study CEMA401A2202, a Phase 2, double-blind, placebo-controlled, randomized trial to determine the safety and efficacy of EMA401 in reducing 24-hour average pain intensity score in patients with painful diabetic neuropathy.

The content of this SAP is based on the final version of protocol CEMA401A2202 (release date 15-Sep-2017). All decisions regarding final analysis, as defined in the SAP document, have been made prior to database lock and unblinding of the study data.

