2.8.1 Adverse events (AEs)

Treatment-emergent adverse events (TEAEs) are defined as any adverse events that develops after initiation of study treatment until the end of study visit or any event already present that worsens following exposure to the study treatment.

If an adverse event starts at the date of week 12 visit it should be allocated to the treatment epoch and not to the treatment withdrawal epoch. Adverse events reported 21 days after end of study date in the scope of USM will not be included in the summary tables, but will be listed.

TEAEs will be summarized (number of cases as a percentage of number at risk) by treatment group separately for Treatment epoch and Treatment withdrawal epoch. Number and percentage of patients with TEAE will be summarized by primary system organ class and preferred term for each treatment group during the double-blind Treatment epoch and during the double-blind Treatment withdrawal epoch. Severity will be classified as "mild", "moderate" and "severe". Serious TEAEs, TEAEs by maximum severity and TEAEs leading to premature discontinuation from study drug will be presented in a similar format as adverse events. Additionally, a listing of patients with TEAE will be presented. Drug abuse-related adverse events (identified using a pre-specified search criterion) will be summarized during the double-blind Treatment epoch. To assess the potential for withdrawal effect, drug abuse-related adverse events will be summarized for the double-blind Treatment withdrawal epoch.

The following additional analysis will be performed.

- Analysis of treatment-emergent adverse events with onset date before 25-Feb-2019

For rash adverse events, following details will be listed:

- Laterality and location of rash

- Did the subject start any new topical non-pharmaceutical products within the last 14 days prior to the start of rash?
- Topical Non-pharmaceutical Products related to the event of rash including soap, detergent, perfume, cologne and lotion.
- Were there any additional contributing factors that may have led to the rash?
- Did the dermatologist agree with the event?
- Additional investigation performed to diagnose that event: yes, no

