Since the NPSI has not been studied in the EMA401-003 study, to mitigate the risk of uncertainty on the value of treatment difference and standard deviation, the effect size (treatment difference/ standard deviation) of NPSI total score has been considered for the calculation of power. The power of the study was calculated for different effect sizes ranging in 0.1, 0.5 for NPSI total score corresponding to 100 mg.

Under the assumptions of a 0.8 point treatment difference between 100 mg b.i.d. and placebo, a standard deviation as 2.6 for the primary efficacy variable and an effect size of 0.4 for 100

[figure not shown]
mg b.i.d. for the key secondary variable, N=200 patients per treatment arm will provide approximately 85% power to show that 100 mg b.i.d. is statistically significant over placebo for the primary efficacy variable, using the testing procedure mentioned in Figure 2-1. The power of showing the statistical significance of 100 mg b.i.d. dose in terms of the key secondary variable will be 84% under the same scenario. If we assume the treatment difference of 0.7 for the NRS as observed in the 4-week PoC study and the effect size for NPSI as 0.35, then the power for the primary objective will be 77% and that for the key secondary objective will be 72%. If the treatment difference between 100 mg b.i.d. and placebo is 0.9 for the NRS, and effect size is 0.45 for 100 mg b.i.d. for the NPSI, the power increases to 94% for the primary objective. The corresponding power for the key secondary objective increases to 93%.

4 Change to protocol specified analyses

An additional population, the mFAS population, has been defined.

The following analyses were specified in the protocol but will not be performed due the early termination of study:

- first and third supplementary analysis to the primary analysis
- tipping point analysis
- supplementary responder analyses
- ANCOVA analyses for BPI-SF, worst NRS pain score, ISI, [REDACTED]
- proportional odds model for PGIC
- analyses regarding maintenance effect of EMA401 over placebo
- time to "sustained" pain reduction
- Apart from analyses of clinical abnormalities summaries of laboratory data, vital signs and ECG intervals have been removed
- Shift tables of laboratory data
- No safety figures will be presented
- Bazett correction for QTc

The following analyses have been added:

- sensitivity analyses on modified full analysis population
- analyses of TEAEs with onset before study termination date

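### After early termination the SAP reports adverse events only as crude percentages, which are too low if read as 12-week risks, most of all for late-onset events

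*Protocol*

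**What the plan says.** Protocol Table 2-1 defines the safety endpoint as "Number and severity of treatment-emergent adverse events and the frequency of adverse events leading to discontinuation", together with the number of serious events. The matching objective covers the whole study and names no 12-week risk.

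Protocol 9.5.2.1 and SAP 2.8.1 use the same measure: "TEAEs will be summarized (number of cases as a percentage of number at risk) by treatment group". The SAP gives it separately for the Treatment and Treatment withdrawal epochs. SAP 2.1 takes as denominator for percentages the number of patients in the relevant population or subgroup, with no reference to time at risk.

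The Amendment 1 section of the SAP reports that "137 patients out of 400 planned patients have been randomized" and refers to "many study treatment discontinuations due to trial termination in the scope of the Urgent Safety Measures". The SAP's Document History records that "Dot plots and Kaplan Meier plots of AEs have been removed", and SAP section 4 adds that "No safety figures will be presented".

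Other parts of the SAP do allow for the truncation:
- SAP 2.5.2 imputes efficacy data under missing at random after a stop due to the Urgent Safety Measures.
- SAP 2.2 and 2.5.4.2 add the mFAS, limited to patients randomized at least 12 weeks before 25-Feb-2019.
- SAP 2.7.2 keeps Kaplan-Meier estimates with Greenwood intervals for rescue medication.

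For adverse events, SAP 2.8.1 adds only an analysis of events with onset before 25-Feb-2019. That is a calendar cut and takes no account of time at risk.

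**The concern.** In a trial where patients are followed for the full Treatment epoch, cases over patients treated is close to a 12-week risk. Once the sponsor's termination cuts some patients short, a patient stopped part-way counts as much in the denominator as a 12-week completer, but had less time in which to have an event. No planned adverse event table corrects for this.

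What is at stake is the absolute risk the trial can report. Protocol 3.3.4 gives 28 days as the longest Phase 2 exposure so far, so Weeks 5 to 12 are the new safety information in patients. Truncation removes follow-up from those weeks first. Allergic dermatitis, hepatic enzyme elevation and neutropenia are named as potential risks in SAP 2.8.1.1, and their percentages would be diluted in the same way.

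**Working it through.** The documents give no adverse event incidence and no share of patients cut short, so there is no plan figure to reproduce. The check is how far a crude percentage falls below the 12-week risk.

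**Share cut short, from the documents' dates.** The first SAP version, dated 16-Feb-2018, preceded the first patient's first visit (SAP Document History). The termination date is 25-Feb-2019 (SAP 2.2). The span is 374 days, or 374/7 = 53.4 weeks. If randomization was uniform over it, patients randomized in the last 12 weeks (after 3-Dec-2018) could not reach Week 12: 12/53.4 = 22.5%, or about 31 of 137. A later start or rising accrual gives more. Randomization that ended before 25-Feb-2019 gives less. I therefore also show 40% and 60%, which are pure assumptions.

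**Formula.** Let R be the true 12-week risk, f the share cut short at a time uniform over 0-12 weeks, and m the average fraction of R already reached at the cut. Then

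crude = (1 - f)R + f·m·R, and relative shortfall = f(1 - m).

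Take R = 10%, so the cumulative hazard is H = -ln(0.9) = 0.1054.
- Constant hazard over 12 weeks: mean risk at the cut = 1 - (1 - e^-H)/H = 1 - 0.1/0.1054 = 5.09%, so m = 0.509.
- Onset only in Weeks 0-4: one third of cuts fall inside the window and two thirds after it, so m = (0.509 + 2)/3 = 0.836.
- Onset only in Weeks 8-12: two thirds of cuts fall before the window, so m = 0.509/3 = 0.170.

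| Onset pattern | f = 22.5% | f = 40% | f = 60% |
|---|---|---|---|
| Constant hazard | 8.9% (11% low) | 8.0% (20% low) | 7.1% (30% low) |
| Weeks 0-4 only | 9.6% (4% low) | 9.3% (7% low) | 9.0% (10% low) |
| Weeks 8-12 only | 8.1% (19% low) | 6.7% (33% low) | 5.0% (50% low) |

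Cells show the expected crude percentage against a true 10%, with the relative shortfall in brackets.

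**Between arms.** With true risks of 10% and 5% and constant hazard in both arms, the crude figures at f = 22.5% are 8.9% and 4.4%: difference 4.5 points, ratio 2.00. At f = 60% they are 7.1% and 3.5%: difference 3.5 points, ratio 2.01. The true values are 5.0 points and 2.00.

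**Does the remedy work?** In 3,000 simulated samples of 137 patients per case, the Kaplan-Meier 12-week incidence, with the termination as censoring, averaged 10.0% for even onset and 10.0-10.1% for onset in Weeks 8-12.

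An exposure-adjusted rate does not repair the late case. With f = 50% and onset spread evenly over Weeks 8-12, the share of events seen is 0.5 + 0.5 × (1/3 × 1/2) = 0.583. Person-time is 0.5 + 0.5 × 0.5 = 0.75 of full. The ratio 0.583/0.75 = 0.78 leaves the rate about 22% low.

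**The case against.** The strongest reply is that the plan never promised a 12-week risk. The endpoint asks for number, severity and frequency, and its objective covers the whole study, so a crude percentage is a correct count of what was seen. This stands as far as it goes: the defect lies in SAP 2.8.1 after termination, not in the protocol endpoint, and it bites when the figure is read as a 12-week risk. With no horizon stated for a 12-week epoch, that reading is likely.

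The truncation will also be visible. SAP 2.4.1 tabulates exposure by arm at thresholds up to 12 weeks, SAP 2.3.1 gives disposition with reasons, and patients with events are listed. These tables show the problem but correct no percentage. The reduced scope was openly declared for an abbreviated report, before lock and unblinding, so an added table is an improvement rather than the repair of a mistake.

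Two stronger readings are tempting. A reader might infer that follow-up ran from a few days upward. The documents give no minimum follow-up and do not say that randomization continued to the termination date. A reader might also infer that the arms are compared unfairly. A single calendar stop in a 1:1 randomized, double-blind trial cuts both arms alike, and no imbalance in early stops is documented. Nor do the documents say what prompted the Urgent Safety Measures.

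**Conclusion.** The point holds for absolute percentages and risk differences, taken as 12-week figures. On average, truncated follow-up without censoring can only pull them down, and the pull is strongest for late onset. The relative comparison is little affected.

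The size is conditional. The shortfall is about 11% at constant hazard and 19% for Weeks 8-12 events if 22.5% were cut short, and about 30% and 50% if 60% were. The 22.5% rests on assumed uniform accrual from the earliest possible start up to the termination date. The onset patterns are assumptions too, and for events in the first four weeks the shortfall is only 4% to 10%. The calculation also treats adverse event observation as ending at the cut. Any follow-up after stopping would lengthen observation, though with time off drug.

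This is a low-cost improvement that changes the absolute risks the trial can report. It does not invalidate the planned safety tables.

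**What to change.** In SAP 2.8.1, before database lock, add one table for the Treatment epoch in the SAF, by arm:
- **Main measure:** the Kaplan-Meier 12-week cumulative incidence with 95% CI, with patients stopped by the termination censored at the end of adverse event observation.
- **Events:** any TEAE, serious TEAEs, TEAEs leading to discontinuation, and allergic dermatitis, hepatic enzyme elevation and neutropenia.
- **Clock:** define the end of adverse event observation once, consistent with the SAP's rule on events reported 21 days after end of study, and use it throughout the table.
- **Supportive only:** patient-years and exposure-adjusted incidence rates on that same clock, labelled as assuming constant hazard.
- **Keep** the crude table beside it.

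The dates needed are already collected, so the cost is one extra table in an abbreviated report and a short wording change. Intervals will be wide. With an even split of 137 patients (68.5 per arm) and a 10% risk, the half-width is 1.96 × √(0.1 × 0.9/68.5) = 7.1 points even with complete follow-up. Rare events will be estimated poorly.
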